isometric contraction followed by blood-flow occlusion) Vs. a control condition (no isometric contraction nor blood flow occlusion), on H-reflex recruitment curve and V wave excitability (aim #1). Since the activation of group III/IV afferents can inhibit the corticospinal pathway (61) we hypothesize that the normalized maximal amplitude and the slope of the ascending limb of the H-recruitment curve will decrease with metaboreflex activation. Additionally, we intend to examine the acute impact of different exercise modalities (resistance, supramaximal and endurance) on nociception sensibility (by the application of a cold tolerance test and by determining pressure pain threshold) (aim #2). This will allow us to investigate the role of different acute exercise paradigms on possible metaboreflex desensitization in its relationship with altered neuromuscular responses at post-exercise time point (attenuated inhibition of H-reflex and V-wave amplitude during metaboreflex activation). Also, once past research has shown that muscle metaboreflex activation reduces the sensitivity of the baroreflex (68), we will measure arterial pressure (AP) and heart rate variability (HRV) during cold pain tolerance testing. Despite all exercise modalities could enhance reducing pain sensibility after exercise, we hypothesize that resistance and supramaximal exercise stimuli will enhance nociceptive tolerance via metaboreflex desensitization compared to that seen with endurance exercise (attenuated increase of AP and sympathetic component of HRV during cold pressor test). Finally, we intend to explore the impact of long-term resistance, supramaximal and endurance training on nociceptive sensibility, using the same tests of aim #2 (aim #3). We hypothesize that chronic EIH will be of greater magnitude after supramaximal and resistance exercise training vs. endurance training. In addition, we hypothesize that decreased nociception will be related with attenuated inhibition of H-reflex and V-wave amplitude and attenuated increase of AP and sympathetic component of HRV during metaboreflex activation after training and this will result in increased exercise performance via heightened H-reflex and V-wave excitability.

2. Research Plan and Methods

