2.3 Aim #3

2.3.1 Participants

We will recruit a total of 30 participants. Sample size is overestimated in order to allow us to accommodate an attrition rate of ~ 20% during follow up, once participants will only be eligible for final testing if they attain at least 85% of the training sessions, with the goal of allocating at least 8 participants to each of the three training groups (G Power 3.0.10 software; to achieve 80% of correctly reject the null hypothesis, based on Jones et al. 2014 (38)). Specific inclusion and exclusion criteria are discussed in

subsection 2.4.1

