2.3.2 Study design

Each intervention group will perform 6 weeks of exercise training (resistance, supramaximal and endurance training). Participants allocated to each training group will be evaluated before and after training. On one day participants will be tested for pressure pain threshold and cold pain tolerance with concomitant measures of AP and HRV. The influence of metaboreflex activation (maintained submaximal isometric contraction followed by blood flow occlusion) on H-reflex and V-wave parameters will also be measured. On another day, participants will be evaluated for resting AP and HRV, neuromuscular adaptations and performance. The experimental design is illustrated in figure 3.

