2.4.13 Statistical analysis (aim #1, #2 and #3)

Normality will be verified through the Shapiro-Wilk test. Univariate ANOVAs will be used to explore differences in the impact of blood-flow occlusion vs. non-blood flow occlusion on each H-reflex and V-wave variable (aim #1). Repeated measures ANOVA will be computed to determine significant main effects for time (pre- vs. post-acute exercise), condition (resistance vs. supramaximal vs. endurance exercise) and time-by-condition interactions on pain tolerance/threshold/ratings, AP, HRV and H-

reflex parameters and V-wave amplitude with metaboreflex activation (aim #2). Repeated measures ANOVA will be computed to determine significant main effects for time (pre- vs. post training), condition (resistance vs. supramaximal vs. endurance training) and time-by-condition interactions on exercise performance, pain tolerance/threshold/ratings, AP, HRV, H-reflex parameters and V-wave amplitude with metaboreflex activation, and neuromuscular adaptations to training (aim #3). Correlations between the impact of exercise or training on pain tolerance/threshold/ratings and performance on H-reflex, V-wave, AP and HRV variables will also be explored. Significance level will be set at $p < 0.05$. All data will be treated using SPSS 25.0 for statistical analysis.

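### Aim #3 has no untrained comparator, so its pre-post time effect, the only test of whether training changed nociception at all, cannot be attributed to training

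*Combined protocol and SAP*

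**What the plan says.** Section 1.3 sets the third aim: "we intend to explore the impact of long-term resistance, supramaximal and endurance training on nociceptive sensibility". It then predicts larger chronic hypoalgesia after supramaximal and resistance training than after endurance training. It also predicts that reduced nociception will go with less reflex inhibition and better performance.

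Section 2.3.2 describes the arms: "Each intervention group will perform 6 weeks of exercise training (resistance, supramaximal and endurance training". The people tested before and after are those allocated to a training group. Section 2.3.1 gives the size: "We will recruit a total of 30 participants", with the goal of "allocating at least 8 participants to each of the three training groups" after an "attrition rate of ~ 20% during follow up".

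For the analysis, section 2.4.13 says: "Repeated measures ANOVA will be computed to determine significant main effects for time (pre- vs. post training". The condition factor has three levels, all of them training modalities, and the time-by-condition interaction is also tested. The outcomes include pain tolerance, threshold and ratings.

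The other two aims do have a comparator. Aim #1 has a control condition without contraction or occlusion (1.3, 2.4.7), and Aim #2 has passive rest (2.2.2). For Aim #3 the text describes no untrained group, control period, familiarisation session for the pain tests or adjustment for retesting.

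**The concern.** The interaction asks whether the modalities differ. It cannot show that any of them had an effect. Within this design the question in the aim, whether training alters nociception, falls to the time main effect, which has no concurrent reference.

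The pain outcomes depend on the participant's own judgement. Pressure threshold is the point at which he reports pain (2.4.8), cold tolerance ends when he withdraws his foot (2.4.9), and ischaemia and cold pain are self-rated (2.4.7.1, 2.4.9.1). A change on the second exposure is possible without any training effect. If all three groups moved together, the result would be a significant time effect and no interaction. That is also the pattern expected if all modalities reduced nociception equally, and the data could not tell the two apart.

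The protocol applies this reasoning to others' work. Section 1.1 tempers a cited finding of reduced laser-evoked potentials after exercise because the reduction did not differ from a passive-rest control. Aim #3 could not make that check on its own results.

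**Working it through.** **1. Is there room for an untrained arm?** Inputs from 2.3.1: three training groups, at least 8 completers each, about 20% attrition. Completers: 3 × 8 = 24. Recruits: 24 / (1 − 0.20) = 30, which matches the stated total. Figure 3 is not available, but this arithmetic leaves no place for a fourth group. The 8 per group cannot be reproduced, because no effect size, SD, correlation or test is given.

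**2. Time main effect under drift alone.** Assume no training effect and the same mean shift in every arm.
- Standardised change: dz = drift / √(2(1 − r)), with drift in SDs of a single measurement and r the pre-post correlation.
- Test: F with 1 and 24 − 3 = 21 df, noncentrality 24 × dz², alpha 0.05 (2.4.13).
- Example: drift 0.3 and r = 0.7 give dz = 0.3 / √0.6 = 0.387, noncentrality 24 × 0.15 = 3.6 and rejection probability 0.44.

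The documents give neither drift nor r, so both are assumed over a range:

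| Drift (SD) | r = 0.5 | r = 0.7 | r = 0.8 | r = 0.9 |
|---|---|---|---|---|
| 0.1 | 8% | 9% | 11% | 18% |
| 0.2 | 15.5% | 23% | 32% | 55% |
| 0.3 | 29% | 44% | 60% | 88% |

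Every cell exceeds 5%. The size depends heavily on the two assumed inputs.

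**3. Interaction under the same drift.** With two time points the interaction is a one-way ANOVA on change scores, F with 2 and 21 df. A shift common to all arms cancels. Simulation with 8 per arm (40,000 runs per setting, common shift from 0 to 0.8 SD of change) gave rejection rates of 4.9–5.2%.

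**4. Power of the interaction.** With noncentrality 24 × f², power reaches 80% at f = 0.68 on change scores. If two modalities shared one mean change and the third differed by δ SDs of change, f = δ√2/3. Then δ = 0.68 × 3/√2, or about 1.4 SDs of change.

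**5. Size of a design with an untrained arm.** Completers: 4 × 8 = 32. Recruits: 32 / 0.8 = 40. With noncentrality d² / (1/n₁ + 1/n₂) and 28 error df, 80% power needs d = 1.19 SDs of change for the pooled trained arms against control (24 vs 8), and 1.45 for one trained arm against control (8 vs 8). Under drift alone this pooled contrast rejected in 4.9–5.1% of simulated runs.

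**The case against.** The strongest reply is that the directional hypothesis in 1.3 concerns differences between modalities, and 2.4.13 plans the interaction that tests it. Step 3 bears this out, so the defect does not reach the between-modality comparison. One qualification: the protection applies to outcomes measured alike in every arm. Exercise performance uses a different test in each group (2.3.4.1 to 2.3.4.3).

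The aim is also worded as exploratory, and nothing in the documents shows that habituation occurs over 6 weeks, which way it would run or how large it would be. That stands. A reader might infer that drift will be present and will be published as chronic hypoalgesia. The documents do not support this. They support only that such drift, if present, could not be told apart from a training effect. Likewise, 88% is one corner of an assumed range and not an estimate for this trial; at 0.1 SD drift the figure is 8–18%.

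A reader might also infer that the whole proposed chain from training to performance fails for this reason. The planned correlations do not depend on mean change in that way: a shift that is the same for everyone moves means and leaves correlations unchanged.

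What the reply leaves unanswered is the aim itself. The interaction cannot establish that training had an impact, and no other planned test does so with a comparator.

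**Conclusion.** The point holds, limited to the time main effect and within-group changes in Aim #3. These are uncontrolled pre-post comparisons and cannot support a claim that training reduced nociception. With 24 completers and no training effect, a common drift of 0.1 to 0.3 SD would make the time effect significant in roughly 8% to 88% of trials. That range rests on assumed drift, an assumed correlation of 0.5 to 0.9, and equal drift in all arms. The absence of a comparator follows from the text and the sample-size arithmetic and needs none of these assumptions. The between-modality test keeps its error rate under common drift but detects only large differences.

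**What to change.** In 1.3 and 2.4.13, state that causal conclusions for Aim #3 will be drawn from the time-by-condition comparison only. State too that time main effects and within-group changes will be reported as uncontrolled pre-post changes that cannot be attributed to training. Add that, with 24 completers, the interaction has 80% power only at about f = 0.68 on change scores, so a non-significant interaction is not evidence that the modalities are equivalent. The restriction presumes random allocation to the arms; the text of 2.3 speaks only of allocation, so this should be made explicit.

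The cost is wording and a narrower conclusion: the trial could say whether modalities differ, but not that training as such produces chronic hypoalgesia.

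If the sponsor wants the broader claim, the direct remedy is an untrained arm tested at the same two times, with trained-versus-untrained change as the test. That takes about 40 recruits instead of 30 and, at 8 completers per arm, would still detect only differences of about 1.2 to 1.5 SDs of change. It is therefore noted as an alternative, not as the required change.

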2.3.4 Exercise Performance

2.3.4.1 Resistance training group

Both before as well as after training, participants will be evaluated for maximal and submaximal knee extension strength. Measurements will be taken in the seated position, with the participants maintaining their knee flexed at 70° (69). MVC will be determined based on the highest peak torque obtained in 3 trials, interspersed by 60 s of passive recovery. Then, participants will be asked to maintain 40% of MVC until failure. Visual feedback from the dynamometer software will be provided. Task termination will occur whenever the participants exhibit strength decrements $\geq 10\%$ for more than 10 s.

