2.3.4.2 Endurance training group

Exercise performance will be determined based on the maximal distance completed by each participant in response to a time-trial run. For the time-trial run, both before and after training, participants will be asked to endure a submaximal treadmill running for as long as possible at the speed compatible with 50% of the distance between the 1st ventilatory threshold and $\text{VO}_{2\text{max}}$ ($\Delta 50$ speed).

Before each time trial, on a different day, participants will complete a treadmill ramp protocol to volitional exhaustion. This test will be used with two specific purposes: 1) to determine participants $\text{VO}_{2\text{max}}$, 1st ventilatory threshold, and the $\Delta 50$

speed; 2) to prescribe the treadmill running speeds for the training period.

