2.3.4.3 Supramaximal training group

Both before as well as after training, participants will perform the maximal number of 30 s maximal all-out cycling trials (70), interspersed by a 4-minute of active recovery period, until mean power value decreases to 50% of the first supramaximal bout.

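### Aim 3 enters exercise performance in one three-group ANOVA although each group takes a different test, so the condition effect and interaction depend on the units of recording

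*Combined protocol and SAP*

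**What the plan says.** Section 2.4.13 specifies, for aim 3, a repeated measures ANOVA with a pre/post time factor, "condition (resistance vs. supramaximal vs. endurance training) and time-by-condition interactions on exercise performance", followed by the pain, cardiovascular and reflex outcomes.

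Sections 2.3.4.1 to 2.3.4.3 define performance separately for each group:

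- **Resistance:** two measures. For strength, "MVC will be determined based on the highest peak torque obtained in 3 trials"; then "participants will be asked to maintain 40% of MVC until failure".
- **Endurance:** "Exercise performance will be determined based on the maximal distance completed by each participant in response to a time-trial run".
- **Supramaximal:** "participants will perform the maximal number of 30 s maximal all-out cycling trials", stopping when mean power has fallen to half that of the first bout.

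No group takes another group's test. Section 2.4.12 normalises H waves, V waves and EMG amplitude, but neither it nor section 2.4.13 gives a common scale for performance or chooses between the two resistance measures. Section 2.3.1 sets the group size, "with the goal of allocating at least 8 participants to each of the three training groups".

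**The concern.** A condition main effect here asks whether torque or hold time, running distance and a number of sprints have the same mean. That question has no meaning. The interaction asks whether their changes are equal in raw units, and the answer depends on whether distance is typed in metres or kilometres.

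Section 1.3 places performance at the end of its proposed chain: reduced nociception goes with less reflex inhibition, and "this will result in increased exercise performance via heightened H-reflex and V-wave excitability". If the ANOVA is run as written, a significant condition effect or interaction on performance could reflect units alone, and a significant time effect could not show which training worked.

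The between-modality hypothesis for aim 3 concerns pain: "We hypothesize that chronic EIH will be of greater magnitude after supramaximal and resistance exercise training vs. endurance training". Those outcomes are measured the same way in every group, so that comparison is not touched.

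**Working it through.** **Inputs from the documents.** Three groups, two time points, significance level 0.05, 8 completers per group. The stated total reproduces: 24/(1 − 0.20) = 30.

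**Assumed inputs (not in the documents).** Hold 180 or 300 s, or torque 150 or 250 Nm; distance 4000–6000 m; 4–6 bouts; between-person CV 20%; SD of log change 0.08 or 0.113; log-normal scores; 20,000 simulated trials per cell. Ranges below are minimum to maximum over this grid.

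**Step 1: the tests.** Let d_g be the mean change in group g (R, E, S), s_g² the variance of change, and d̄ the mean of the three d_g.

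- Interaction: F = [8 Σ(d_g − d̄)² / 2] / [(s_R² + s_E² + s_S²)/3], on 2 and 21 df.
- Time: F = 24 d̄² / [(s_R² + s_E² + s_S²)/3], on 1 and 21 df.
- Condition: the interaction formula applied to each person's average of pre and post.

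**Step 2: change one unit.** Recording one group's test in another unit multiplies its d_g by c and its s_g² by c², and leaves the other groups alone. All three F ratios change. For example, take baselines of 300 s, 5000 m and 5 bouts with a 10% gain in each group. The mean changes are 30, 500 and 0.5 in s/m/bouts, but 0.5, 0.5 and 0.5 in min/km/bouts.

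**Step 3: the limit when metres dominate.** If d_R, d_S, s_R and s_S are negligible, then d̄ = d_E/3 and Σ(d_g − d̄)² = (4/9 + 1/9 + 1/9) d_E² = (2/3) d_E².

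- Interaction F → [8 × (2/3)/2] d_E² / (s_E²/3) = 8 d_E²/s_E².
- Time F → 24 (d_E/3)² / (s_E²/3) = 8 d_E²/s_E².

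Both become the endurance group's own paired t², which has 7 df, judged against critical values for 21 df (3.47 and 4.32). With no gain they reject with probability P(|t₇| > 1.86) = 10.5% and P(|t₇| > 2.08) = 7.6%. The other two groups hardly count.

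**Step 4: simulated rejection rates for the interaction** (hold time as the resistance measure; gains in the order resistance/endurance/supramaximal).

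| True gains | s/m/bouts | min/km/bouts | log(post/pre) |
|---|---|---|---|
| none | 10–11% | 5–6% | 5% |
| 10/10/10% | 66–91% | 5–24% | 5–6% |
| 20/0/20% | 10–13% | 68–100% | 81–99.5% |

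The lower end of the last cell allows for bouts being whole numbers.

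With torque as the resistance measure, changing only metres to kilometres moves the interaction from 10–12% to 99–100% for 20/0/20% gains, and from 99–100% to 10–11% for 0/20/0% gains.

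**Step 5: the other two effects.**

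- Time rejects in 5–8% with no gain and 63–100% with equal 10% gains, but in only 8–11% for 20/0/20% gains in s/m/bouts.
- Condition, with no gain anywhere, rejects in 5% to 100% depending on baselines and units.

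**A single data set shows the same thing.** With assumed means of 200 s, 6 bouts and 5000 m, CV 20%, pre-post correlation 0.8 and 10% gains, one simulated sample gave an interaction p of 0.00004 in s/bouts/km and 0.90 in min/bouts/km.

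**The case against.** **The percentages rest on assumptions.** This is true. At 240 s, 5000 m and 5 bouts, raising the SD of log change from 0.08 through 0.113 and 0.20 to 0.25 lowers the equal-gain interaction rate in s/m/bouts from 90% to 66%, 33% and 25%. The 20/0/20% rate in min/km/bouts falls from 99% to 86%, 38% and 26%. The sizes shrink; the dependence on units remains.

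**Equal relative gains are not the null of a raw-scale interaction.** Also true, so the 66–91% is not a type I error rate. With no gain, the interaction's error is only about double the nominal 5%. The strongest case of a result produced by units alone is the condition effect.

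**No stated hypothesis needs a between-group test of performance.** The proposed chain runs from nociception to performance, and the planned correlations address it more directly. This limits the harm. It also means that dropping the between-group test loses little, and that pooling raw performance scores in those correlations would bring the same fault back.

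**A relative score may have been intended.** The plan does not say so, and a pre/post time factor takes two scores, not one percentage change.

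**The log ratio does not settle everything.** The hold is set relative to MVC, the running speed comes from a ramp test done before each time trial, and the cycling test stops relative to its own first bout. If these references are re-set after training, a real gain may not appear in the ratio. The supramaximal section also describes a procedure without naming the score to be analysed, although a bout count is the natural reading. These points stand as refinements to the fix.

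**Conclusion.** The concern holds: the analysis is wrong as written for exercise performance. That its condition effect and interaction depend on units is algebra and needs no assumed input. How often this misleads depends on assumed baselines and spreads. Over the grid used, the interaction rate for the same true gains ranges from about 5% to 91% or from about 10% to 100% according to units. The time effect is close to valid as evidence that some group changed, but it does not identify the group, and in metres it mostly misses gains outside the endurance group.

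The damage is confined to performance. The other aim 3 outcomes, the between-modality pain hypothesis and the total of 30 are unaffected. The point should be fixed before analysis.

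**What to change.** Remove exercise performance from the aim 3 ANOVA sentence in section 2.4.13 and add: *Exercise performance will be analysed within each training group as log(post/pre) with a 95% CI; no condition main effect on performance will be tested.*

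In addition:

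- For the resistance group, name either peak torque or hold time, or list both as separate outcomes. Confirm that the bout count is the supramaximal score.
- State whether the hold load and running speed are kept or re-set after training.
- If a time-by-condition test is kept, run it on log(post/pre) and say that it compares relative gains on different tests.
- If performance change enters correlations that pool the groups, use the log ratio with training group as a factor.

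**Cost.** Wording only, with no new visit, test or participant. The raw-scale between-group test is lost, and three or four separate within-group estimates raise a multiplicity question that the report should acknowledge.

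Precision is limited. The half-width on the log scale is 2.365 × SD/√8, which is 0.067 for SD 0.08 and 0.095 for SD 0.113. An observed 10% gain would then have a 95% CI of about 3% to 18%, or 0% to 21%. For whole-number bouts the SD can reach 0.148 (half-width 0.124), giving about −3% to 24%.

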1.2 Analgesia and Performance

The mechanisms underlying neural changes in response to specific experimental interventions can be investigated by measuring reflex responses, namely the H reflex and V wave (46). Despite both responses are under the influence of common neural mechanisms, H-reflex is more sensitive to changes in the intrinsic motoneuron properties and presynaptic inhibition (46, 47, 48), while the V-wave is more sensitive to modifications in supraspinal input to the motoneuron pool (49, 50). In addition, they are task and training dependent (51, 52, 53). Longitudinal studies have revealed positive changes in H-reflex after endurance (52) and Wingate-based training (53), which reflects improvements in spinal excitability. Resistance training has been shown to increase V-wave amplitude (51, 52) which is representative of increased supra-spinal neural drive.

Recent studies suggest that fatigue development may be related, at least in part, with nociception (54), and it may play a role in exercise tolerance (1). During exercise, ascending group III and IV muscle afferents discharge in response to noxious, metabolic and mechanical stimuli within the contracting skeletal muscles to regulate nociception, muscle activation and peripheral fatigue development (55, 56). As exercise-induced nociception is present in nearly all forms of time-dependent competition, the requirement for understanding its influence on performance and how athletes respond to its presence is imperative (1). Thus, the ability of an athlete to tolerate exercise-induced nociception is a critical factor in successful sports performance (54). If neuromuscular signals are consciously interpreted as nociceptive, leading to adjustments in pace or intensity, then individuals with heightened pain tolerance may be able to generate higher levels of muscle power (1). If nociception acts as a moderator of “allowed” exercise intensity, then the mechanisms that affect the level of pain tolerance may theoretically enhance performance by enabling an athlete to exercise beyond the normal protective threshold (eliciting a greater metabolic stress) (57).

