2.2.2 Study design

In a randomized and crossover trial, on 2 different days, participants will be tested before and after performing acute bouts of different exercise modalities or

passive rest. Participants will be tested for: (1) pressure pain threshold, (2) cold pain tolerance with concomitant measures of AP and HRV, (3) the influence of metaboreflex activation (maintained submaximal isometric contraction followed by blood flow occlusion) on H-reflex and V-wave excitability. For those enrolled in endurance and resistance exercise modalities, participants will visit the laboratory on a previous day for $VO_{2\text{max}}$ and maximal repetition assessments for rigorous exercise prescription on experimental day. The experimental design is illustrated in figure 2.

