2.4.5 Standard H-recruitment curves (aim#3)

Before and after long-term training, standard methods will be used for M-wave and H-reflex recordings (52). These measurements will be taken while each participant maintains a submaximal low intensity contraction of the plantar flexors (10% MVC) with visual feedback from the dynamometer software being provided. The upper current intensity will be determined, firstly, by progressively increasing the current intensity by 5 mA from 0 until there is no further increase in peak torque or in peak-to-peak M-wave amplitudes. At each intensity level, three stimuli will be delivered at 3-seconds intervals. To construct the H-recruitment curves, the upper current intensity (compatible with maximal M-wave) will be divided into 22 segments equally separated on a logarithmic scale, with 16 stimuli/intensity randomly applied to construct the recruitment curves, delivered at 3s intervals.

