into 22 segments equally separated on a logarithmic scale, with 4 stimuli/intensity, to limit the time under ischemia (~4 min), randomly applied to construct the recruitment curves, delivered at 3s intervals. After 2 min rest, the isometric plantar flexion contraction will be repeated with subsequent thigh circulatory occlusion. V waves will be ~~delivered~~ during 5 MVCs with 15 s of rest between trials (63) to limit the time under ischemia (~2 min), via supramaximal electrical stimulation (150% of the current needed to evoke maximal M wave; 1-ms single square pulse) delivered to the tibial nerve when torque exceeds 90% MVC. In control condition of aim #1 this H-reflex and V-wave collecting procedure will also be used but without sustained isometric contraction followed by blood flow occlusion. In aim #2 it will be assessed 15-30 min post-exercise or rest.

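### Aims #2 and #3 hypothesise reduced reflex inhibition, but the planned tests use activated-state values only and never compare them with unactivated values

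*Combined protocol and SAP*

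**What the plan says.** **Hypothesis.** Section 1.3 expects acute exercise to produce "attenuated inhibition of H-reflex and V-wave amplitude during metaboreflex activation". For Aim #3 it links lower nociception to less reflex inhibition under metaboreflex activation, and then to better performance through higher H-reflex and V-wave excitability. Reduced inhibition and raised excitability are thus two separate links in one chain.

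**Analysis.** In section 2.4.13 the reflex outcome for Aim #2 is H-"reflex parameters and V-wave amplitude with metaboreflex activation (aim #2"). For Aim #3 the list ends with "H-reflex parameters and V-wave amplitude with metaboreflex activation, and neuromuscular adaptations to training (aim #3"). The ANOVA factors are time and exercise or training modality. Activation state is not a factor, and section 2.4.12 derives no difference or ratio between states. Only Aim #1 contrasts occlusion with no occlusion.

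**Recordings, Aim #3.** Section 2.4.5 provides unactivated curves: "Before and after long-term training, standard methods will be used for M-wave and H-reflex recordings". Section 2.4.6 does the same for V waves. Section 2.4.13 does not define neuromuscular adaptations, but the term reasonably covers these recordings.

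**Recordings, Aim #2.** Section 2.2.2 lists "3) the influence of metaboreflex activation (maintained submaximal isometric contraction followed by blood flow occlusion) on H-reflex and V-wave excitability". Sections 2.4.5 and 2.4.6 are labelled Aim #3 only. Section 2.4.7 gives the version without contraction and occlusion for one place: "In control condition of aim #1 this H-reflex and V-wave collecting procedure will also be used but without sustained isometric contraction".

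**Expected general effects of training.** Section 1.2 states: "Longitudinal studies have revealed positive changes in H-reflex after endurance (52) and Wingate-based training (53"). It also reports higher V-wave amplitude after resistance training.

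**The concern.** An activated-state amplitude can rise for two reasons: activation suppresses the reflex less, or the reflex is larger in every state. Only the first is metaboreflex desensitisation. The plan's own background leads one to expect the second after training, and to expect it to differ by modality: H-reflex after endurance and Wingate-type training, V wave after resistance training. A time effect or a time-by-modality interaction on the activated value could therefore appear with inhibition unchanged.

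The mechanistic conclusion is what is at stake. The planned correlations of pain and performance changes with H-reflex and V-wave variables have the same ambiguity wherever they use activated values.

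**Working it through.** The plan gives no figure to reproduce here. It states no mean, SD, correlation or expected gain for the reflexes, so the numbers below illustrate the size of the problem under stated assumptions.

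**Step 1. Which states are recorded and compared.**

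| Aim | Activated | Unactivated | States compared in 2.4.13 |
|---|---|---|---|
| #1 | yes | yes (2.4.7, control condition) | yes |
| #2 | yes | none in the text | no |
| #3 | yes | yes (2.4.5, 2.4.6) | no |

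**Step 2. Time-by-modality test on the activated value.** From the plan: 8 per group (2.2.1; target in 2.3.1), three groups, alpha 0.05. Assumed: H/Mmax 0.50 standard and 0.40 activated, so inhibition is 20% before and after; a proportional rise *g* in both states in two groups and none in the third; SD of the pre-post change σ = 0.08 or 0.12.

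The activated value rises by δ = 0.40*g* in two groups. The interaction is a one-way F test on the change, with 2 and 21 degrees of freedom (critical value 3.47) and noncentrality

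λ = 8 × [2(δ/3)² + (2δ/3)²] / σ² = (16/3)(δ/σ)².

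- σ = 0.08: λ = 1.33, 5.33, 12.0 for *g* = 10, 20, 30%, so 15, 47, 83% of trials are significant.
- σ = 0.12: λ = 0.59, 2.37, 5.33, so 9, 23, 47%.

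**Step 3. Alternatives that use the standard recording.** Simulation with 20,000 trials per setting, σ = 0.08, correlation 0.7 between the changes in the two states, inhibition unchanged:

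| General rise | Activated only, time-by-modality | Raw scale, state-by-time-by-modality | Raw scale, state-by-time | Log ratio |
|---|---|---|---|---|
| 10% | 15% | 6% | 8% | about 5% |
| 20% | 47% | 9% | 17% | about 5% |
| 30% | 83% | 14% | 33% | about 5% |

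The raw-scale contrast drifts because a 20% rise adds 0.10 to the standard value (0.50 to 0.60) but 0.08 to the activated value (0.40 to 0.48). The gap widens from 0.10 to 0.12, which looks like *increased* inhibition. The ratio stays at 0.48/0.60 = 0.80.

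**Step 4. Time effect when all groups rise alike.** With 24 participants and a general rise of 0.3, 0.5 or 0.8 SD of the change, the t test on the activated value (23 degrees of freedom, noncentrality 1.47, 2.45, 3.92) is significant in 29, 65 and 96% of trials.

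**Step 5. How well the two Aim #3 recordings match.** Stimulation takes 22 × 16 × 3 s = 1,056 s (17.6 min) for the standard curve and 22 × 4 × 3 s = 264 s (4.4 min) for the activated curve. Rest between V-wave MVCs is 1 min against 15 s. The 10% MVC background contraction is stated only for the standard curve. Section 2.3.2 appears to put the two on different days.

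**The case against.** **The unactivated data exist in Aim #3.** A reader might infer that Aim #3 examines the reflexes only under activation, or that the investigators would take any rise for reduced inhibition. The documents support neither. Sections 2.4.5 and 2.4.6 record the unactivated state at both time points, a general rise should be visible there, and section 1.3 itself expects higher excitability. What stands is narrower: two parallel ANOVAs do not test whether the two changes differ. A significant result in one state and a non-significant one in the other, with about 8 per group, is not evidence that inhibition changed.

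**Aim #2 is one acute bout.** The studies cited in section 1.2 for these rises concern training, so they cannot be used to predict a general acute rise. That is correct. The Aim #2 point is only that an acute general change, in whatever direction, cannot be told apart from a change in inhibition. The passive-rest day does not resolve this: the text gives it no unactivated recording either, and rest is not a level of the condition factor in 2.4.13. Nor should a reader conclude that an unactivated recording is certainly absent, because Figure 2 is not shown.

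**An added state factor would not be a clean remedy.** This also stands. On the raw scale it is biased under a proportional rise (step 3); with a correlation of 0.9, the state-by-time rate at a 30% rise is about 74%.

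**The recordings are not matched.** Their differences cancel in a pre-post comparison only if their effect is the same before and after training. Recovery between maximal efforts, for example, may itself change with training.

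**Conclusion.** The point holds in this form: for Aims #2 and #3 no planned test addresses inhibition, because activated values are never compared with unactivated ones. In Aim #3 the data are collected and the test is missing. In Aim #2 the text gives no data for such a test. This follows from the wording of 1.3, 2.4.5 to 2.4.7 and 2.4.13, and does not depend on the simulation.

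The size does depend on assumptions. A purely general rise of 10 to 30% in two of three groups is flagged in 15 to 83% of trials at an SD of change of 0.08, and in 9 to 47% at 0.12. These are not error rates of this trial, since the plan gives no reflex variability. The roughly 5% for the log ratio rests on a proportional rise. If the rise were the same absolute amount in both states (0.50 to 0.60 and 0.40 to 0.50), the ratio would move from 0.80 to 0.83, and the raw difference would be the stable measure.

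**What to change.** **Aim #3, section 2.4.13.** Define the outcome for reduced inhibition as the per-visit log of activated over standard value, for Hmax/Mmax, slope and V/Msup. Test it for time and time-by-modality. Keep the activated-only analysis as descriptive. Do not use a raw-scale state factor as the main test; the raw difference may be reported as a sensitivity analysis, with proportionality stated as an assumption. Use the log ratio in the correlations that concern inhibition. Define neuromuscular adaptations so that it is clear that the standard curves and V waves are included.

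State as a limitation that the two recordings differ in stimuli per intensity (16 against 4), V-wave rest (1 min against 15 s), apparently in day, and possibly in background contraction, and that these differences cancel only if their effect is the same before and after training.

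**Aim #2.** Limit the conclusion to reflex size under metaboreflex activation. If an unactivated recording is in fact made, describe it and use the same ratio.

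**Cost.** Wording in the analysis section, with no new recordings. A ratio can be noisier than a single amplitude. With the SDs of step 3 as log-scale approximations (0.08/0.40 = 0.20 activated, 0.08/0.50 = 0.16 standard), the variance of the log-ratio change is 0.0656 − 0.064ρ, against 0.04 for the activated value alone. It is therefore noisier when the correlation ρ between the two changes is below 0.4, which is possible if the recordings fall on different days. For the curve parameters, each participant also needs four curves that meet the r-square rule of section 2.4.12 (two states at two visits) instead of two.
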